5.3 LIFESTYLE CONSIDERATIONS

Smoking cessation.

5.4 SCREEN FAILURES

These subjects will be monitored longitudinally per standard of care for any signs of stroke/TIAs or other neurological deterioration including cognitive decline. If during the study period, the subjects re-meet the criteria of inclusion, then they will be approached again for enrollment.

5.5 STRATEGIES FOR RECRUITMENT AND RETENTION

Recruitment

Participants will present to either to the emergency department and/or neurosurgery/neurology clinic for evaluation of symptomatic chronic cervical internal carotid artery (ICA) occlusion (COICA). Imaging studies will be obtained to confirm diagnosis of COICA.

To be recruited and enrolled for the trial, the following inclusion/exclusion criteria must be satisfied:

E.2 Inclusion and Exclusion Criteria:

Inclusion Criteria	Exclusion Criteria
Age ≥ 21	History of Moyamoya or Moyamoya like disease
Complete occlusion of cervical ICA on imaging studies (MRA or CTA) and confirmed with DSA	Tandem occlusion
History of TIA or stroke	No evidence of penumbra (increased MTT and/or PTT) on CT perfusion [◊]
Increased MTT and/or TTP on CTP as defined as TMax threshold of $> 10cc > 4$ seconds in the territory of the occluded carotid specifically in the MCA territory when compared to the opposite unaffected hemisphere	Severe co-morbid diseases: end-stage renal disease, liver cirrhosis, COPD requiring home oxygen, terminal illness such as cancer, Parkinson disease or other neurodegenerative diseases,

	severe congestive heart failure, seizures, debilitating stroke, mRS ≥ 3 .
All occlusion is due to atherosclerotic disease	Short life expectancy due to cancer or other co-morbid diseases
MoCA < 26 and/or one or more abnormal test on the rest of the neuropsychological battery administered at screening	MoCA ≥ 26 and normal screening battery [❖]
Study team able to gain consent from subject or LAR	Subject unwilling to participate in follow up and/ or unwilling to be randomized to surgery [❖]
Class A or B occlusion based on COICA classification	Class C or D occlusion based on COICA classification [❖]
	Occlusion of the Common Carotid Artery

❖ If a subject meets any combination of these exclusion criteria, they may be applicable for the non-randomized third arm.

E.3 Definitions:

- Chronically Occluded Cervical ICA (COICA): documented complete occlusion of cervical ICA evident on CTA, and/or MRA for at least 4 weeks.
- Symptomatic (COICA): subjects with chronically occluded ICA with a presentation of TIA and/or stroke corresponding to anatomical structures supplied by the ipsilateral COICA.
- Abnormal test is considered 1.5 SD below age, gender, and education norms
- Severity of impairment
 - Mild cognitive impairment: MoCA score < 26 but ≥ 23
 - Moderate cognitive impairment: MoCA score < 23 but ≥ 18
 - Severe cognitive impairment: MoCA < 18

I. The proposed NIA SCORE trial is committed to aggressively recruit and include women and members of minority groups.

II. MINORITY RECRUITMENT

The investigators have set a goal of enrolling at least 15-30% of minorities in this trial. To ensure adequate recruitment and enrolment of minorities to the trial, we will employ the following strategies:

1. The research team will be educated and made aware of the attention that must be given to cultural, historical, social, and political factors that may influence minority participation. In focus groups with African-Americans, many of them needed clarification of a clinical trial, and the term “research study” had more meaning. Most indicated that certain criteria had to be in place before they would consider participating: benefit to family/community, pastor’s encouragement, type of research, understanding of study, and who is conducting the research.
2. Social workers will be involved to help arrange for transportation for these study subjects who lack them, which is important for follow-up in clinic.
3. Clinic office hours may need to be extended to allow for the schedules of working individuals or those with caregiving responsibilities.
4. The accessibility and location of the clinic/hospital would also be considered to encourage compliance with follow-up appointments.

III. RECRUITMENT OF WOMEN:

The investigators have set a goal of enrolling at least 30-50% women in this trial. The staff and investigators will make it a priority to make extra time and commitment to understand other issues in the subject's personal life that may affect her enrollment and compliance.

IV. Specific strategies that we will use to enhance recruitment and retention of underrepresented minorities and women into your trial:

The research team will employ the following additional strategies to ensure adequate enrolment of women and minorities in the trial by suing these specific strategies:

1. The research team will be urged to appropriately present the trial to women and all minority patients with emphasis on presenting the facts in regard to the potential impact of the study on their health and standard care.
2. The nurse research coordinator will periodically communicate with women and minority subjects to address their concerns and attempt to facilitate compliance and retention and minimize drop out.
3. Financial voucher (\$75) per annual clinic visit will be provided to cover gas mileage, parking, and a small meal.

6 STUDY INTERVENTION

6.1 STUDY INTERVENTION(S) ADMINISTRATION

6.1.1 STUDY INTERVENTION DESCRIPTION

Endovascular balloon angioplasty and stenting

Medical management: Aspirin 325 mg po daily; Plavix 75 mg po daily; Statin.

6.2 MEASURES TO MINIMIZE BIAS: RANDOMIZATION AND BLINDING

- 1) Randomized 1:1 ratio
- 2) Blinded assessment of cognition, MRI and exploratory endpoints

6.3 STUDY INTERVENTION COMPLIANCE

Percent revascularized

6.4 CONCOMITANT THERAPY

Best Medical Management: daily dual antiplatelet therapy (aspirin: 325 mg p.o. qd and Clopidogrel: 75 mg p.o. qd), optimization of systolic blood pressure (120 -140 mmHg), smoking cessation, and statin therapy. These primary risk factors (systolic blood pressure, smoking, and cholesterol level) will be managed mainly by the local primary care physician with inputs from the research team. The goal is targeting a systolic blood pressure (SBP) 120-140 mmHg and smoking cessation. Subjects will be monitored by the primary care physician after enrollment and then every four months for management

of risk factors during the first year, then annually thereafter. Also during follow up visits, the research team will ensure compliance with medications.

Also keeping the SBP > 120mmHg will ensure prevention of potential hypoperfusion of the brain resulting into cerebral hemodynamic compromise and potential TIA and/or stroke.

Statin: the subject will be started on Lipitor 20 mg po qd. Lipid profile will be monitored by the primary care physician.

Smoking Cessation: We chose a target level of complete cessation of smoking in our trial for the following reasons: 1. Several studies have shown that smoking is associated with worsening atherosclerotic disease and stroke. 2. Smoking cessation is recommended for all patients by the US Department of Health and Human Services and by the AHA/ASA guidelines for the Primary Prevention of stroke. and management of UIA. 3. Light and intermittent smoking have been associated with increased cardiopulmonary and cerebrovascular risks and death. If the patient doesn't quit smoking, he/she will continue to be encouraged to quit smoking and he/she will be kept enrolled in the study.

To insure compliance with recommendation and best medical management plan, we will implement the following: A) The study will provide each subject with a blood pressure cuff to measure blood pressure in sitting position biweekly and document pressure measurements in a diary notebook. These measurements will be taken at home and in clinic. The measurements will be reviewed by the PCP of the study, the research nurse, and local PCP. Family member will be educated on how to take the blood pressure. The nurse research will observe the family member perform BP measurements on the subject during the initial training and in random visits to ensure adequate technique. B) Counting bills by the research team during clinic visits will be used to monitor for compliance. C) Lipid profile panel will be used to monitor compliance for using statin. D) A survey of over the counter medications will be obtain during each clinic visit.

7 STUDY INTERVENTION DISCONTINUATION AND PARTICIPANT DISCONTINUATION/WITHDRAWAL

7.1 DISCONTINUATION OF STUDY INTERVENTION

None

7.2 PARTICIPANT DISCONTINUATION/WITHDRAWAL FROM THE STUDY

Participants are free to withdraw from participation in the study at any time upon request.

An investigator may discontinue or withdraw a participant from the study for the following reasons:

- Pregnancy
- Significant study intervention non-compliance
- If any clinical adverse event (AE), laboratory abnormality, or other medical condition or situation occurs such that continued participation in the study would not be in the best interest of the participant
- Disease progression which requires discontinuation of the study intervention such as development of cancer, severe COPD, end stage renal disease, ...
- If the participant meets an exclusion criterion (either newly developed or not previously recognized) that precludes further study participation.

The reason for participant discontinuation or withdrawal from the study will be recorded on the REDCap Case Report Form (CRF). Subjects who sign the informed consent form and are randomized but do not receive the study intervention may be replaced. Subjects who sign the informed consent form, and are randomized and receive the study intervention, and subsequently withdraw, or are withdrawn or discontinued from the study, will not be replaced.

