1 PROTOCOL SUMMARY

1.1 SYNOPSIS

Title: Neurocognitive Impairment Assessment in Symptomatic Carotid Occlusion Recanalized Endovascularly

Study Description: This is a phase 2 randomized single-center open label clinical trial with randomization of 1:1 to either best medical management vs. best medical management and endovascular revascularization of COICA. The study will utilize best medical management and will randomize patients to endovascular balloon angioplasty and stenting.

- A third study group will be included that meet selected exclusion criteria. This group will not be randomized, only eligible for best medical management and prospective observation.

Objectives:

Primary Objective:

To test the hypothesis that endovascular revascularization of COICA improves significantly cognitive function assessed by a specifically designed battery of 14 cognitive tests including the Montreal Cognitive Assessment (MoCA).

Secondary Objective:

To test the safety of endovascular revascularization of chronically occluded ICA.

Tertiary/exploratory Objectives:

To test the hypothesis that subjects with symptomatic COICAs and mild/moderate cognitive dysfunction have the following biomarkers:

- A) Presence of lactate and decreased Naa/Cr in the watershed area (specifically centrum semiovale) on 1H-MRI-spectroscopy, and
- B) Decreased size of the hippocampus and amygdala on MRI.
- C) increased MTT and/or PTT on CTP in the ipsilateral side of the occluded ICA specifically in the MCA territory when compared to the opposite unaffected hemisphere.

Endpoints:**Primary endpoints:**

1. Cognitive outcome at 12-month follow-up assessed mainly by a specifically designed battery of 14 cognitive tests including the MoCA.

Secondary Endpoints:

1. Safety: Occurrence of Stroke, Cerebral Hemorrhage, or Death

Exploratory endpoints:**Biomarkers:**

1. Resolution/improvement of previously increased of MTT and/ or PTT (normalization of MTT/ PTT) on CTP specifically in the ipsilateral MCA territory.

2. The presence/absence of lactate on 1H-MRI spectroscopy in centrum semiovale in the ipsilateral side of COICA;

3. The change in size of amygdala and hippocampus in the ipsilateral side of COICA.

4. Subgroups: Gender difference

Age ≥ 21**Study Population:**

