2. TIA: New neurological deficits that resolve within 24 hours of onset and within 120 days prior to enrolment.
3. Abnormal neuropsychological test: any tests included in the screening battery that is scored below 1.5 SDs below the gender, age, and education matched norms.

Procedure:

Procedure will be performed under general anesthesia. Prior to induction of general anesthesia, A-line will be placed to monitor for blood pressure. The mean arterial pressure (MAP) will be maintained above 80mmHG during the procedure till complete revascularization of the occluded cervical ICA. At that time MAP will be lowered to < 80mmHG. The anesthesia team will use their standard of care medications to maintain the pressure as described above.

The groin area will be prepped and draped in the usual sterile fashion. Femoral access will be obtained using 18 gauge needle. Nine French sheet will be placed over the guide wire provided. 5 French Bernstein catheter and 6 French Cook shuttle catheter will be advanced over 0.038 Terumo guide wide to the common carotid artery of the occluded cervical ICA. At the time, the 5 French Bernstein catheter will be withdrawn and contrast will be injected to obtain selective images. After that, attempt to cross the occluded segment will be done, first using SL-10 microcatheter and 0.014 synchro soft microwire, if unsuccessful, then will use the 0.038 exchange Terumo guide wire. If not successful, then will use the stiffer end of the 0.038 exchange Terumo guide wire. If not successful, then abort procedure. If successful, then advance the microwire or the Terumo wire across the occlusion till identifying normal lumen. Following that, angioplasty and stenting using approved angioplasty balloons and carotid stents will be used to recanalize the occluded ICCA. During that time, anesthesia will monitor for bradycardia. If any bradycardia, they treat per standard care and use atropine. Once recanalization is achieved, the MAP will be lowered to < 80mm Hg using standard care medication per anesthesia. IV maintenance dose Tirofiban (0.1 microgram/kg/min) immediately post procedure as a monotherapy for the first 24 hour. Following that the puncture site will be closed using angioseal device. The patient will be extubated and transferred to surgical ICU for BP monitoring. If the subject is doing well, he/she is transferred to the normal floor. Aspirin and plavix will be continued for 12 months.

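### Section 7.2 allows withdrawal from the study for undefined non-compliance and secures no outcome data afterwards, so failed recanalizations could drop out of the intention-to-treat comparison

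*Combined protocol and SAP*

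**What the plan says.** Section 7.2 introduces its list with "An investigator may discontinue or withdraw a participant from the study for the following reasons". One entry is "Significant study intervention non-compliance", with no threshold and no statement of whether it means the procedure, the medication or both. Another is "Disease progression which requires discontinuation of the study intervention", which treats stopping the intervention and leaving the study as one step. The section then adds: "Subjects who sign the informed consent form and are randomized but do not receive the study intervention may be replaced". Section 7.1, on discontinuing the intervention, contains the single word None.

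Section 6.3, on compliance with the intervention, reads in full "Percent revascularized". The procedure description in 4.1 ends the sequence of crossing attempts with "If not successful, then abort procedure" and does not say whether such a patient counts as having received the intervention. Section 6.1.1 lists medical management beside stenting. Section 6.4 monitors it ("Counting bills by the research team during clinic visits will be used to monitor for compliance", plus a lipid panel and a blood pressure diary) without limiting this to one arm.

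Section 1.1 states: "This is a phase 2 randomized single-center open label clinical trial with randomization of 1:1". Section 4.1 has the principal investigator alone perform the procedure, and 6.2 blinds the assessment of cognition. Sections 9.3 and 9.4.1 specify ITT. The primary model in 9.4.2 takes MoCA change at 6 and 12 months as its outcome.

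**The concern.** The ITT question is what a policy of attempting revascularization does to cognition, and failed attempts are part of the answer. Section 7.2 lets someone who knows both the arm and the angiographic result end a patient's participation on an undefined ground. Blinded testing does not protect against this, because the selection happens before the test. A patient withdrawn before month 6 contributes no outcome to the model. Recanalization status is not in the model, so the model cannot correct for selection on it. Section 9 states no sensitivity analysis for missing outcomes.

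If failures left the surgical arm, that arm would drift towards successfully revascularized patients only, while the control arm has no matching filter. With 19 patients per arm, a few removals could matter to the go/no-go decision on phase 3 described in 2.1.

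**Working it through.** **The plan's own figure.** Section 9.2 assumes a 2-point difference, SD 2, 80% power and 10% dropout; 9.4.2 gives two-sided 0.05. A two-sample t-test needs 16.7, so 17 per arm, or 34 in total. Then 34 / 0.9 = 37.8, so 38, or 19 per arm. Both stated totals reproduce.

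**Failure rates the documents support.**
- Types A and B, which 5.1 makes eligible: 9.2 states 100% success. The pilot in 2.2 had 8/8 in each type, 16/16 together. The exact two-sided 95% upper limit for 0 failures in 16 is 1 − 0.025^(1/16) = 0.206.
- Types A to C, which 9.2 plans for: 93% success, so 7% failure. This matches (8 + 8 + 0.8 × 8) / 24 = 0.933.

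**Bias formula.** Let f be the share of the surgical arm whose recanalization fails. Assume that successes gain 2 points over control, failures gain 0, both have the same underlying prognosis, and every failure is removed.
- ITT effect = 2(1 − f)
- Estimate with failures removed = 2
- Relative overstatement = f / (1 − f)

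| f | Source | Expected failures of 19 | ITT effect | Overstatement |
|---|---|---|---|---|
| 0 | stated A/B success | 0 | 2.00 | 0 |
| 0.07 | 93% in 9.2 | 1.3 | 1.86 | 0.14 points, 7.5% |
| 0.206 | upper limit, 16/16 | 3.9 | 1.59 | 0.41 points, 26% |

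At f = 0.07 the chance of at least one failure among 19 is 1 − 0.93^19 = 0.75.

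**Sensitivity to prognosis.** Suppose the procedure has no effect and patients whose recanalization fails would in any case end 2 points worse (an assumption; the documents give no such figure for types A and B). Removing them creates an apparent benefit of 2f: 0.14 points at f = 0.07 and 0.40 at f = 0.20. In simulation (8,000 runs, 17 per arm) the two-sided type I error was about 5.5% and 7.6%. The first is barely distinguishable from 5%.

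**The case against.** The strongest reply is that no passage classes a failed recanalization as non-compliance. A percentage revascularized reads naturally as an arm-level summary, and it needs the failures in its denominator. Section 7.2 is permissive, and 4.1 says only that the procedure is aborted. Other text favours retention: ITT is stated twice, 7.3 expects 12 months of follow-up, 8.1 plans three test occasions for enrolled participants, and 6.4 keeps patients who continue smoking in the study. For a one-time procedure, None in 7.1 is unsurprising. All of this stands. It makes the route a possible reading rather than a rule, but none of it says what happens to the cognitive tests once an investigator has withdrawn someone.

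A reader might infer several stronger things that the documents do not support:
- That the withdrawal clause acts on the surgical arm alone. It does not; both arms receive monitored medical management. Only the failed-procedure ground is one-sided.
- That the pilot shows failures to have a poor prognosis, since 4 of 10 had a later TIA or stroke. All ten failures were types C or D, which 5.2 excludes from randomization, and the outcome was not cognition.
- That the 70% literature success rate in 2.2 sets the expected failure rate. That review was not restricted to types A and B.
- That any adverse event allows withdrawal. Section 7.2 limits this to events that make continued participation contrary to the participant's interest.

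**Conclusion.** The gap is real and conditional. An undefined ground lets an unblinded investigator end study participation, no follow-up is secured afterwards, and this undercuts the stated ITT analysis. Failed or aborted recanalization could fall under that ground or under the replacement rule, and both of those routes are confined to the surgical arm.

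The effect could be overstated; the documents do not show that it will be. The 7.5% rests on a success rate that includes type C, and the 26% rests on a confidence limit, not an expected rate. Both assume that every failure is removed and gains nothing, so with equal prognosis they are upper cases for each failure rate. Replacement does harm only if the replaced patient is also left out of the analysis, a point on which 7.2 is silent.

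**What to change.** 1. Delete non-compliance from the grounds in 7.2 for withdrawal from the study.
2. State in 7.1 and 7.2 that an aborted or unsuccessful recanalization, or non-adherence to medical management, is not study withdrawal. Such participants, while they consent, stay in their randomized arm, complete the existing 6- and 12-month cognitive assessments and are analysed as randomized.
3. State that replacing a participant does not remove that participant from the ITT set.
4. Leave the participant-protection grounds (adverse events judged on best interest, pregnancy, exclusion criteria) in place for clinical decisions. Outcome assessments should still be sought where the participant consents and it is appropriate. Letting only withdrawn consent, death or lost contact end follow-up would go too far, because it would cancel these grounds.
5. Report revascularization success (6.3) descriptively.
6. Reconcile 5.1 (types A or B) with 9.2 (A, B or C), since this sets the expected failure rate.

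The cost is protocol wording, with no new visits or procedures. The estimated effect may be slightly smaller because failures are counted. Under the assumptions above, power at 17 per arm is 81% with no failures, 75% at 7% failure and 62% at 20%.

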7.3 LOST TO FOLLOW-UP

Enrolled subjects in the study are expected to be followed for 12 months post intervention. The followup included assessment of cognitive function using the designed battery of tests (including Moca), DSA, CTP and MRI of the brain.

Participants are considered lost to follow-up when they stop reporting to scheduled study visits and cannot be reached to complete all protocol-required study procedures.

To minimize that:

The following actions must be taken if a participant fails to return to the clinic for a required study visit:

- The research nurse will attempt to contact the participant and reschedule the missed visit within 30 days from scheduled visit and counsel the participant on the importance of maintaining the assigned visit schedule and ascertain if the participant wishes to and/or should continue in the study.
- Before a participant is deemed lost to follow-up, the PI will make every effort to regain contact with the participant (where possible, 3 telephone calls and, if necessary, a certified letter to the participant's last known mailing address or local equivalent methods). These contact attempts will be documented in the participant's medical record or study file.
- Should the participant continue to be unreachable, he or she will be considered to have withdrawn from the study with a primary reason of lost to follow-up.

